Pharmacological therapy plays a key role in the secondary prevention of CVD and improve long term outcomes particularly in patients who have not undergone revascularization via percutaneous coronary intervention (PCI) (2–4). Large evidence supports drugs conferring mortality benefit from several different classes: antiplatelet agents, angiotensin-converting enzyme inhibitors (ACEIs)/angiotensin receptor blockers (ARBs), beta blockers and lipid-lowering drugs (5–7).

Adherence to secondary prevention medications following acute coronary syndromes (ACS) is a predictor of future major adverse cardiovascular events. Medication usage (and its success) requires the coordination of the behaviours of both treating physicians and patients, particularly with regards to adherence. Underutilisation of these medications is associated with higher risk of major adverse cardiovascular events globally (8). Patients' poor adherence to their medication is a complex problem for health care services, especially in the care of heart diseases, for which the correct and effective treatment is essential for a patient's quality of life and survival rate(9). A study had shown that patients who recently experienced a myocardial infarction (MI) and did not adhere closely to their prescribed regimen were 2.6 times more likely to die within a year following the MI compared with those who followed their regimen more closely (10).

Medication adherence has been studied extensively over the past decades. Numerous reports in the literature had estimated that by 12 months, adherence to cardioprotective therapy had dropped to less than 50% across several classes of drugs including statins and ACE-Inhibitors(11). Some of the predictors of non-adherence most often cited include polypharmacy, frequency of medication changes, socioeconomic status, cost, household composition, comorbidity, and accessibility to medical care (12). Gaining an understanding of the key factors that influence adherence among patients post-ACS may allow treating physicians to tailor their treatment approach and implement effective hospital interventions to improve patient adherence and, subsequently, CV outcomes(13).

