In summary, this study is essential for understanding why patients in Nepal fail to adhere to life-saving medications post-ACS and what can be done to mitigate this problem, ultimately improving patient care and reducing the burden on the healthcare system.

5. Objectives

a. General objectives:

To assess the level of adherence to prescribed secondary prevention medications and identify the factors influencing adherence among patients with Acute Coronary Syndrome (ACS) in Nepal.

b. Specific objectives:

- **To assess the level of adherence to secondary prevention medications (SPMs) among patients discharged after an Acute Coronary Syndrome (ACS) event, including antiplatelets, statins, beta-blockers, and ACE inhibitors/ARBs.**
- **To explore the influence of patient demographic factors** (such as age, gender, education level, occupation, and place of residence) and clinical characteristics (type of ACS, comorbidities) on medication adherence.
- **To identify patient-reported barriers to medication adherence**, including concerns about medication side effects, pill burden, practical issues with medication administration, and difficulties in integrating medications into daily routines.
- **To evaluate the relationship between medication adherence and clinical outcomes**, such as recurrent cardiac events, rehospitalization.

6. Research questions/hypothesis

- What is the level of adherence to secondary prevention medications among Acute Coronary Syndrome (ACS) patients in Nepal, and what demographic, clinical, and patient-reported factors influence this adherence and its associated clinical outcomes?

7. Research design and Methodology

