7.7 Inclusion and Exclusion criteria

- **Inclusion Criteria:**

1. Patients diagnosed with ACS, including ST-Elevation Myocardial Infarction (STEMI), Non-ST-Elevation Myocardial Infarction (NSTEMI), or Unstable Angina within the last 12 months.
2. Patients aged 18 years and older.
3. Patients willing to participate and provide informed consent for the study.

- **Exclusion Criteria:**

1. Individuals who have not been diagnosed with ACS or those with other acute or chronic conditions that might influence medication adherence unrelated to ACS.
2. Patients with cognitive impairments or mental health issues that prevent them from understanding or responding accurately to the study questionnaires.
3. Patients with severe chronic conditions (e.g., terminal illness, advanced dementia) that may affect their ability to adhere to medication regimens.

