7.10 Tools and techniques for data collection

- Tools:

Questionnaire

The questionnaire is composed of six simple-to-complete sections.

Section 1:

- Patients provide essential contextual information about the medicines they are taking, when they are administered each day, and their understanding of why they are taking them.
- This helps clinicians compare a patient's actual medication usage with documented clinical records and uncover any medication changes since discharge.

Subsequent sections (Section 2-6):

- These sections use Likert scales instead of binary yes/no responses, which improves the quality of information gathered.
- For example, it allows the assessment of the frequency of non-adherence behaviors rather than just detecting non-adherence.

Section 2:

- Explores overall understanding and satisfaction with medicines.
- Patients respond to four statements regarding their understanding of why their medicines were prescribed and how well they think they are working, using a four-point Likert scale (strongly agree, agree, disagree, strongly disagree).

Sections 3–5:

- Assess specific modifiable barriers to adherence, using the same four-point Likert scale as section 2.
- A free-text box allows patients to specify which medicines their concerns involve.

Section 3:

- Explores three areas of anxiety about medicines (e.g., concerns about medicines causing more harm than good or feeling there are too many medicines).

Section 4:

- Examines four practical concerns associated with medicine-taking (e.g., difficulties with swallowing pills or obtaining repeat prescriptions).

Section 5:

- Assesses three issues related to fitting medicines into the patient's daily routine (e.g., forgetfulness or inconvenience).
- These issues are linked to non-adherence and can potentially be addressed in clinical practice.

Section 6:

- Focuses on adherence to each individual secondary prevention medication (SPM) over the past month.
- It uses a modified version of the SQ tool and a five-point Likert scale.
- Patients are considered non-adherent if they select any answer other than 'all of the time' for any SPM.

[figure not shown]
Technique:

- A relevant questionnaire will be developed and distributed to our research team. They will visit cardiology outpatient department (OPD) as well as in the cardiology ward in Manmohan

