Cardiothoracic Vascular and Transplant Centre to administer and fill the questionnaire, asking patients who meet the research criteria the necessary questions.

- Prior to participation, participants will receive comprehensive information regarding the study's objectives, procedures, and potential risks and benefits. They will be assured that their personal information will remain confidential and solely utilized for research purposes.
- Participants are expected to provide truthful and accurate responses to all study inquiries and protocols.
- The questionnaire will be individually distributed to each participant.

7.13 A graphic outline of the study design and procedures using a flow diagram including the timing of assessments.

8. Plan for data management and statistical analysis

- Information on how the data will be managed (data handling and coding for computer analysis, monitoring and verification).
- Procedures for accounting for any missing or spurious data etc.
- The statistical methods and tests proposed to be used for the analysis of data.
- For projects involving qualitative approaches, specify in sufficient detail how the data will be analyzed.

9. Biases

- Selection Bias: The adherence behaviors of OPD patients may differ significantly from those of re-hospitalized patients. Re-hospitalized patients might have more severe conditions, leading to differences in adherence patterns. This could introduce bias in comparing adherence rates across both groups.
- Survivor Bias: Re-hospitalized patients represent those who have survived a second cardiac event. This excludes patients who may have suffered more severe outcomes or death, potentially skewing the findings.

- **Self-Reported Data:** The reliance on patient self-reports for adherence may introduce recall bias or social desirability bias, where patients overestimate their adherence to appear compliant.

10. Limitations of the study

- **Heterogeneity of Patient Conditions:** Re-hospitalized patients might have more complex medical histories or complications, while OPD patients might represent a more stable cohort. This could lead to difficulties in interpreting results uniformly across both groups.
- **Single-Centre Study:** Conducting the study in one tertiary care hospital limits the generalizability of the findings to other settings, such as rural or private healthcare facilities.

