Yes, human participants are required in this research. The study aims to assess adherence to secondary prevention medications among patients who have experienced Acute Coronary Syndrome (ACS). This research requires direct data collection from individuals who have been prescribed such medications to understand their adherence patterns, factors influencing adherence, and potential barriers. The insights gained from these participants will contribute to improving post-ACS care in Nepal and reducing the risk of recurrent cardiac events.

- Clearly indicate the participant's responsibilities in the research. What is expected of the research participants during the research?
 - **Providing informed consent:** Participants will be fully informed about the purpose, procedures, and potential risks and benefits of the study before deciding whether or not to participate.

- **Completing study procedures:** Participants should be willing to fill out the questionnaire.
- **Protecting their own privacy:** Participants should be aware that their personal information will be kept confidential and only used for the purposes of the study
 - **Protecting the confidentiality of others:** Participants should not disclose any information about other participants or the study to anyone outside of the research team.
 - **Providing honest and accurate responses:** Participants should provide honest and accurate responses to all study questions and procedures.

- Are vulnerable members of the population required for this research? If yes, offer justification.

No

- Are there any risks to the involved participants? If yes, identify clearly what are the expected risks for the human participants in the research and provide a justification for these risks.

No

- Are there any benefits to participants? If yes, identify clearly what are the expected benefits for the participants.

Indirect Benefits to Healthcare: Participants contribute to research that aims to improve post-ACS care and enhance medication adherence strategies, potentially benefiting future patients.

Personal Satisfaction: Patients may feel a sense of fulfillment by contributing to research that could improve public health and the care of other ACS patients.

Awareness and Self-reflection: By participating, patients may gain a better understanding of the importance of medication adherence, which could positively influence their own adherence behaviors.

18. Informed consent

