	c. I have difficulties or problems getting my repeat prescriptions and would like help ordering them from my GP or pharmacy.				
	d. I have difficulties or problems reading the label on the medicines bottle or box and would like a solution or alternative.				

Section 5: Fitting medicines into daily routine	a. I sometimes forget to take my heart medicines.				
	b. I am finding it difficult to fit one or more of my heart medicines into my daily routine.				
	c. I feel inconvenienced/bothered about sticking to all my heart medicines.				

Section 6: Adherence to Individual SPMs

For each of your prescribed medicines (SPMs), please indicate how often you have taken them as prescribed in the PAST MONTH:

Medication	All of the Time	Nearly All of the Time	Most of the Time	About Half the Time	Less than Half the Time
Aspirin					
ACE Inhibitor (e.g. Ramipril, Lisinopril,)					
Beta Blocker (e.g. Acebutalol)					
Medication 4 Statin (e.g. Simvastatin)					
ARIIA (e.g. Candesartan)					

Section 4: Clinical Outcomes

1. **Have you experienced any of the following since discharge?** (Check all that apply)
 - Recurrent chest pain
 - Rehospitalization for cardiac issues
 - Stroke
 - Heart failure symptoms
 - No major events
2. **Follow-up with healthcare provider since discharge:**
 - Yes
 - No
 - If Yes, how many visits: _____

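### The number of SPM classes prescribed is built into adherence status, yet 7.7 does not require any to be prescribed and the outcome comparison does not account for it

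*Combined protocol and SAP*

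**What the plan says.** The population is described in terms of prescription in two places. Section 17 states: "This research requires direct data collection from individuals who have been prescribed such medications to understand their adherence patterns". The general objective in Section 5 is "To assess the level of adherence to prescribed secondary prevention medications and identify the factors influencing adherence".

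Eligibility is not. The first inclusion criterion in 7.7 is "Patients diagnosed with ACS, including ST-Elevation Myocardial Infarction (STEMI), Non-ST-Elevation Myocardial Infarction (NSTEMI), or Unstable Angina within the last 12 months"; the other two are age and consent. No exclusion criterion mentions prescribing.

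The only scoring rule is in 7.10, on questionnaire Section 6: "Patients are considered non-adherent if they select any answer other than 'all of the time' for any SPM". Being adherent is not separately defined. The annexed Section 6 grid is introduced with "For each of your prescribed medicines (SPMs), please indicate how often you have taken them as prescribed in the PAST MONTH" and has five frequency columns, none for a medicine that was not prescribed. On blank entries, Section 8 holds only a template prompt: "Procedures for accounting for any missing or spurious data etc".

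The fourth specific objective is "To evaluate the relationship between medication adherence and clinical outcomes". The Introduction supplies the premise that makes prescribing relevant to it: "Underutilisation of these medications is associated with higher risk of major adverse cardiovascular events globally", after noting that use of these medicines depends on physicians as well as patients.

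**The concern.** Two consequences follow from reading 7.7 and 7.10 together.

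First, an ACS survivor with no SPM prescribed is eligible, cannot be classed as non-adherent, and has no stated place in the denominator. Adherence to prescribed medicines is not defined for that patient.

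Second, and more important, the rule requires a perfect answer on every SPM. With one SPM a patient has one way to fail; with four there are four. The number of classes prescribed is thus related to adherence status by the rule itself. If it is also related to the risk of recurrent events or rehospitalisation, as the Introduction's premise suggests, a pooled comparison of adherent with non-adherent patients mixes the effect of taking medicines with the effect of having been prescribed more or fewer of them. The fourth objective is where this could mislead.

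**Working it through.** **1. The plan's own figure.** 7.6 uses z = 1.96, p = 0.925, d = 0.05: 1.96² × 0.925 × 0.075 / 0.05² = 106.6 (printed 106.39, used as 106), and 106 × 1.10 = 116.6, so 117. The stated totals reproduce. The sample was sized for one proportion, not for an outcome comparison, and the point below does not change it.

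**2. How the rule depends on the number prescribed.** Assume each class is taken perfectly with the same probability q, independently, so the chance of being adherent on k classes is q^k.
- If four-class adherence is 0.925 (the planning value), q = 0.925^(1/4) = 0.981. For 1, 2 and 3 classes the rule gives 0.981, 0.962 and 0.943.
- If four-class adherence is 0.50 (the Introduction cites levels below 50%), the same steps give 0.841, 0.707 and 0.595.

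**3. Headline rate.** Let u be the share with no SPM (assumed 1-5%; the documents give no figure) and p the adherence of treated patients. If no-SPM patients are counted as adherent, the observed rate is u + (1 − u)p, a shift of u(1 − p).
- p = 0.925: 0.01 × 0.075 = 0.08 points to 0.05 × 0.075 = 0.38 points, in percentage points.
- p = 0.50: 0.01 × 0.50 = 0.5 points to 0.05 × 0.50 = 2.5 points.

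**4. Outcome comparison, equal underlying risk.** None of these inputs is in the documents: 0/1/2/3/4 classes prescribed in 3/7/20/35/35% of patients; each class taken perfectly with probability 0.93, independently; event risk 0.5 × 0.75^j when j classes are taken.
- Adherent on k classes: probability 0.93^k, risk 0.5 × 0.75^k.
- Non-adherent on k classes: risk [0.5 × 0.7675^k − 0.93^k × 0.5 × 0.75^k] / (1 − 0.93^k), where 0.7675 = 0.07 + 0.93 × 0.75.

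| Classes (k) | Share | P(adherent) | Risk, adherent | Risk, non-adherent | Ratio |
|---|---|---|---|---|---|
| 0 | 0.03 | 1.000 | 0.500 | none | none |
| 1 | 0.07 | 0.930 | 0.375 | 0.500 | 1.33 |
| 2 | 0.20 | 0.865 | 0.281 | 0.379 | 1.35 |
| 3 | 0.35 | 0.804 | 0.211 | 0.288 | 1.37 |
| 4 | 0.35 | 0.748 | 0.158 | 0.219 | 1.38 |

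The Mantel-Haenszel ratio across k is 1.37. Pooling over k gives 0.274 / 0.233 = 1.18. Dropping the no-SPM patients lowers the adherent risk to 0.2225, so the pooled ratio is 0.2744 / 0.2225 = 1.23. An eligibility line alone therefore recovers only part of the gap.

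**5. Outcome comparison, underlying risk varying with k.** Keep everything else and multiply the untreated risk by a factor g for each class prescribed. The overall level cancels in the ratio.

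| g | Pooled ratio | Stratified ratio |
|---|---|---|
| 1.00 | 1.18 | 1.37 |
| 1.20 | 1.30 | 1.37 |
| 1.33 | 1.37 | 1.37 |
| 1.50 | 1.44 | 1.37 |

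The bias vanishes near 1/0.75 = 1.33, where the higher underlying risk of patients prescribed more classes offsets the assumed benefit per class. Above that it reverses.

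**6. Precision.** Under step 4 the non-adherent share is 0.189, so 0.189 × 106 is about 20 patients against 86. The standard error of the log ratio is √[(1 − 0.274)/(20 × 0.274) + (1 − 0.233)/(86 × 0.233)] = 0.41, which puts a 95% interval of about 0.52 to 2.65 around 1.18.

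**The case against.** A reader might infer that the plan counts untreated patients as adherent. It does not say so. Only non-adherence is defined, the Section 6 grid addresses prescribed medicines, and a patient with no rows could equally be treated as not assessable. What stands is that no rule settles the matter.

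A reader might also infer that under-treated patients are misclassified. They are not: someone who takes the one prescribed SPM perfectly is correctly adherent to prescribed medication, which is what the general objective asks about. The issue is confounding of the outcome comparison, not an error in the adherence label.

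7.8 does list pill burden, as a number of medications. That is close, but it appears as a patient-reported factor for adherence, it is not a count of SPM classes, and nothing assigns it to the fourth objective. Section 10 admits that confounding may be hard to account for, but names access, comorbidities and socio-economic conditions, not prescribing.

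The Section 17 sentence answers an ethics prompt and is not an eligibility criterion. That is fair, but the general objective carries the same restriction. It is also true that, with about 20 non-adherent patients, the study could not distinguish 1.18 from 1.37. That limits what the fourth objective can show under any analysis; it is no reason to leave a built-in confounder out of it.

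**Conclusion.** The point holds as a gap between the stated population and 7.7, and as a confounder created by the scoring rule for the fourth objective. A tempting stronger reading is that the comparison is pulled towards no effect. The documents do not support that: they say underuse is associated with higher risk, but not whether patients prescribed fewer classes were at higher or lower risk to begin with. In the illustrative model the pooled ratio ranges from 1.18 to 1.44 against about 1.37 stratified. These values rest on assumed prescribing shares, independent taking at 0.93 per class and a 0.75 risk multiplier, and they are not bounds. If patients prescribed fewer classes had the higher underlying risk, the pooled ratio would fall below 1.18.

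The effect on the headline adherence rate is small at the planning value and arises only if no-SPM patients are counted as adherent. The change is worth making mainly for the outcome comparison.

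**What to change.** (a) Add to 7.7 that at least one of antiplatelet, statin, beta-blocker or ACE inhibitor/ARB was prescribed after the qualifying ACS. This keeps patients for whom adherence is undefined out of the denominator.

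(b) Add the number of SPM classes prescribed (1 to 4) to the clinical characteristics in 7.8. Take it from the medical record review planned in 7.9, cross-checked against the current-medicines table (MYMEDS Section 1) in the annexed proforma. The record matters because that table covers medicines being taken, so one that was prescribed but stopped could be absent. In the fourth objective, compare outcomes by adherence within, or adjusted for, this number.

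(c) Report each class's adherence among patients prescribed that class. The record-based list also separates a Section 6 row left blank because the medicine was not prescribed from one left unanswered.

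The cost is one eligibility line and one variable derived from data already planned. A few patients become ineligible, and the adjusted estimate is slightly less precise, which should be acknowledged given the small number of non-adherent patients likely.

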 - 4. Semi-skilled worker**
 - Factory or workshop laborer, laboratory or library attendant, car cleaner

5. Unskilled worker

- Watchman, peon, domestic servant, rickshaw puller

6. Unemployed

9. **Family Monthly Income (NPR):** _____

- $\geq 97,451$
- 48,751–97,450
- 36,551–48,750
- 24,351–36,550
- 14,551–24,350
- 4,851–14,550
- $\leq 4,850$

10. **Place of Residence:**

- [] Rural
- [] Urban

11. **Distance from Healthcare Facility:** _____ (km)

Section 2: Clinical Information

1. **Type of ACS:**

- [] ST-Elevation Myocardial Infarction (STEMI)
- [] Non-ST-Elevation Myocardial Infarction (NSTEMI)
- [] Unstable Angina

2. **Date of ACS Diagnosis:** _____

3. **Treatment Received:**

- [] Percutaneous Coronary Intervention (PCI)
- [] Coronary Artery Bypass Grafting (CABG)
- [] Medical Management Only

4. **Comorbidities:**

- [] Hypertension
- [] Diabetes Mellitus
- [] Dyslipidemia
- [] Chronic Kidney Disease
- [] Stroke
- [] Peripheral Arterial Disease
- [] Others (Specify): _____

Section 3: Assessment of Adherence**MYMEDS Questionnaire****Section 1: Current Medicines**

Serial Number	Name of Medicines	Administration Time (Morning/Afternoon/Evening/Night)	Reason for Taking Medicine
1	Antiplatelets	_____	_____
2	Statins	_____	_____
3	Beta-blockers	_____	_____
4	ACE inhibitors/ARBs	_____	_____
5	Others (Loop diuretics, Nitrates, specify)	_____	_____

Section Number	Statement	Strongly agree	Agree	Disagree	Strongly disagree
Section 2: Understanding and satisfaction with medicines	a. I fully understand my heart medicines and why they were prescribed.				
	b. My heart medicines seem to be working for me.				
	c. I feel convinced of the importance of all my heart medicines.				
	d. At least occasionally, I need to alter my medicines on my own to make them work or meet my expectations.				

Section 3: Concerns about medicines	a. I worry that one or more of my medicines will do me more harm than good.				
	b. I feel concerned about being prescribed too many medicines.				
	c. I sometimes alter my medicines by cutting back or stopping taking them. (e.g. due to feeling worse, getting worried or for any other reason)				
Section 4: Practical issues that may be a barrier to adherence	a. I have difficulties or problems opening the medicine bottles or blister packs and would like a solution or an alternative.				
	b. I have difficulties or problems swallowing my medicine(s) and would like a solution or an alternative.				
	c. I have difficulties or problems getting my repeat prescriptions and would like help ordering them from my GP or pharmacy.				
	d. I have difficulties or problems reading the label on the medicines bottle or box and would like a solution or alternative.				

Section 5: Fitting medicines into daily routine	a. I sometimes forget to take my heart medicines.				
	b. I am finding it difficult to fit one or more of my heart medicines into my daily routine.				
	c. I feel inconvenienced/bothered about sticking to all my heart medicines.				

Section 6: Adherence to Individual SPMs

For each of your prescribed medicines (SPMs), please indicate how often you have taken them as prescribed in the PAST MONTH:

Medication	All of the Time	Nearly All of the Time	Most of the Time	About Half the Time	Less than Half the Time
Aspirin					
ACE Inhibitor (e.g. Ramipril, Lisinopril,)					
Beta Blocker (e.g. Acebutalol)					
Medication 4 Statin (e.g. Simvastatin)					
ARIIA (e.g. Candesartan)					

Section 4: Clinical Outcomes

1. **Have you experienced any of the following since discharge?** (Check all that apply)
 - Recurrent chest pain
 - Rehospitalization for cardiac issues
 - Stroke
 - Heart failure symptoms
 - No major events
2. **Follow-up with healthcare provider since discharge:**
 - Yes
 - No
 - If Yes, how many visits: _____

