7.9 Expected time and duration of the study

The study is expected to be completed in 12 months, divided as follows:

- **Months 1-2:** Ethical approval, recruitment of research assistants
- **Months 3-8:** Data collection (patient interviews, medical record review).
- **Months 9-10:** Data entry and analysis.
- **Months 11-12:** Report writing, dissemination of results, and publication

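### The form does not record which secondary prevention medicines were prescribed and has no answer for a stopped one, so a stopped medicine left blank is not counted as non-adherence

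*Combined protocol and SAP*

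**What the plan says.** Section 6 of the MYMEDS form (Annex 1) asks: "For each of your prescribed medicines (SPMs), please indicate how often you have taken them as prescribed in the PAST MONTH". It has preprinted rows for aspirin, ACE inhibitor, beta blocker, statin and ARIIA, and five answer columns. The lowest is 'Less than Half the Time'. There is no column for a medicine that was stopped or never prescribed.

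The scoring rule is in section 7.10: "Patients are considered non-adherent if they select any answer other than 'all of the time' for any SPM".

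The only medicine list on the proforma is headed "Section 1: Current Medicines". Section 7.10 describes its content as the patient's own account: "Patients provide essential contextual information about the medicines they are taking". It adds that this helps clinicians compare use with the records and "uncover any medication changes since discharge". Section 7.9 schedules "Data collection (patient interviews, medical record review" but names no items to extract. No field in Annex 1 holds the discharge prescription or the current one.

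Section 11 lets participants skip questions that make them uneasy. Section 8, which should cover missing data, contains only template prompts.

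**The concern.** The first specific objective is the level of adherence among patients discharged after ACS, covering four classes. That needs a denominator: the SPMs each patient was meant to be taking. Section 6 refers to prescribed medicines, but nothing on the form says which those are, so the denominator rests on what the patient still regards as prescribed.

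The rule in section 7.10 acts only on a selected answer. If a patient has given up one SPM, that row is left blank, and the others are marked at the top category, the patient is adherent under the rule. Complete self-discontinuation can then be recorded as adherence. The same patients would sit in the adherent group when adherence is related to barriers and to outcomes such as rehospitalization, which would blur those comparisons too.

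**Working it through.** **What a blank row can mean.** Reading the form against the rule in section 7.10:

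| Situation for one SPM | What the form can show | Effect of the rule |
|---|---|---|
| Never prescribed | blank | none |
| Stopped by a clinician | blank | none |
| Skipped | blank | none |
| Stopped by the patient, row left blank | blank | none: adherent if all other rows are at the top category |
| Stopped by the patient, lowest category ticked | 'Less than Half the Time' | non-adherent |

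The first four rows look identical. Blanks will also be routine: the form gives ACE inhibitor and ARIIA a row each, while the objectives and section 7.8 treat ACE inhibitors/ARBs as one class. A patient prescribed only one of the two properly leaves the other row empty. The analyst therefore cannot count every blank as non-adherence, and has nothing on the form to sort the blanks.

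**The plan's own figure.** Inputs from section 7.6: z = 1.96, p = 0.925, d = 0.05.

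n = z² × p × (1 − p) / d² = 1.96² × 0.925 × 0.075 / 0.05² = 106.6. The plan states 106.39, taken as 106, so the figure is reproduced to within rounding. Adding 10%: 106 × 1.10 = 116.6, or 117, as stated. (The printed substitution line uses other numbers. That is a separate matter.)

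**Illustration of size.**
- Expected recorded as non-adherent: 106 × 0.075 = 7.95, about 8 patients.
- Shift from 5 unrecorded stoppers: 5 / 106 = 4.7 points.
- 95% half-width at n = 106: 1.96 × √(0.925 × 0.075 / 106) = 5.0 points.

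Let s be the share of all patients who stopped an SPM, have that row blank, and are at the top category elsewhere. If recorded adherence is 92.5%, true adherence is 92.5% − s, and the share of truly non-adherent patients missed is s / (7.5% + s). The values of s are assumptions, because the documents give no discontinuation rate.

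| s (assumed) | Patients of 106 | True adherence | Non-adherent patients missed |
|---|---|---|---|
| 2% | 2.1 | 90.5% | 2 / 9.5 = 21% |
| 5% | 5.3 | 87.5% | 5 / 12.5 = 40% |
| 10% | 10.6 | 82.5% | 10 / 17.5 = 57% |
| 20% | 21.2 | 72.5% | 20 / 27.5 = 73% |

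**The case against.** The strongest reply is that the form can already capture a stopper. The rows are preprinted, and section 7.5 has the researcher ask every question, so the patient need not volunteer the medicine. Taking none of a prescribed SPM fits 'Less than Half the Time', which scores as non-adherent. This stands, and it makes the loss possible rather than built in. It does depend on the patient still regarding the medicine as prescribed, because an interviewer without the prescription cannot tell which rows must be answered. Section 7.1 also allows an online survey, where no one would query a blank.

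A second reply is that stopping is asked about elsewhere: MYMEDS item 3c covers cutting back or stopping, and item 2d covers altering medicines on one's own. True, but these are general agree/disagree items that name no medicine in the answer scale, and neither enters the section 7.10 rule.

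A third is that section 9 already concedes the weakness: "The reliance on patient self-reports for adherence may introduce recall bias or social desirability bias". That concerns inaccurate answers. Here a fully truthful patient can be misclassified. Likewise, the comparison with records in section 7.10 describes what the tool offers clinicians. It is not tied to a form field or to scoring.

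Two stronger readings should be resisted. A reader might infer that adherence is asked only for medicines the patient lists as current. Section 6 says prescribed medicines, and nothing links it to the current-medicines list. A reader might also multiply up an assumed 2–5% stopping rate per class: 0.925 × 0.98⁴ = 85% and 0.925 × 0.95⁴ = 75%. Those results require that every patient is on four classes, that stopping is independent across classes and of other non-adherence, and that every stopper's row is left blank. If only half are left blank, they become 0.925 × 0.99⁴ = 89% and 0.925 × 0.975⁴ = 84%. The documents support none of these inputs.

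**Conclusion.** The point holds as a gap in the measurement of the main outcome. The prescribed SPMs are not recorded, the scale cannot separate stopped from not prescribed, and the scoring rule is silent on blanks. Where a self-stopped SPM is left blank, the error runs in one direction, towards overstated adherence. Whether and how often that happens cannot be read from the documents.

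The shift of about 4.7 points for five such patients is an illustration of sensitivity, not an estimate of the bias. It rests on the 92.5% planning value, which section 7.6 takes from a different instrument (the 4-item MGL scale) and which may not apply under the all-or-nothing MYMEDS rule. It shows that with about 8 recorded non-adherent patients, a handful of unrecorded ones matters. The change is worth making because it is cheap.

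**What to change.** 1. During the record review already scheduled in section 7.9, copy into the proforma the SPM classes on the discharge prescription and on the most recent prescription. Both are needed: Section 6 covers the past month, while the ACS event may be up to 12 months earlier, so the discharge list alone may be out of date.
2. Add to each Section 6 row 'not prescribed' and 'no longer taking it (stopped by clinician / by self)'. Keep these apart from the existing five-point scale so that the MYMEDS result can still be reported.
3. Score against the prescribed list. A still-prescribed SPM stopped by the patient counts as non-adherent. A clinician-stopped or never-prescribed SPM leaves the denominator. A blank for a prescribed SPM is missing, not adherent.
4. Write the blank-row rule into section 8, and report the adherence proportion with unresolved blanks counted first as adherent and then as non-adherent.

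The cost is a few more fields and some extraction time. Section 7.4 already cites access to detailed records. The documents do not say that every index discharge was from this centre, and section 10 acknowledges incomplete records, so some discharge prescriptions will not be obtainable. Those patients should be reported separately.
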